#### **6.14 Photographs at injection sites**

After the injection it is possible, in some patients, to see the gold as a small grey mark under the skin less than 5mm across and this may still be there for 3 months or more after the injection. In some individuals there may be a painless red area around the grey mark which may also stay there for 3 months or more. We intend to take photographs of the injection sites at each visit to compare the marks at subsequent visits.

#### **6.15 Contact hypersensitivity or skin patch testing**

Contact hypersensitivity testing or patch testing is to determine delayed Type 4 hypersensitivity to allergens including gold for this study. We would like to check for development of hypersensitivity to gold in patients who received trial medication. This is an optional test performed anytime post-dose (referring to post final dose). The test itself can involve 3 visits. For the participant's convenience, visit 2 can be done at home by the patient. These visits include day 0 (patches applied to back or arm of patient), day 2 (patches taken off (home or clinic) and first reading (if in clinic)) and final reading (day 4 or day 7). We are looking for red, raised, itchy, vesicular reactions to detect contact allergy and these results are graded according to internationally agreed standards. The allergens applied have to be diluted to correct dilutions considered suitable by experts for patch testing and application to patients' backs. The patient needs to keep the back (or other site of application for example the arm) dry during the whole test period and be prepared to attend all 3 visits to perform the test. Participants will be asked for blood sample (5ml) to measure serum gold concentration before the test.

#### **6.16 Sample management**

Sample management will be carried out according to GCP and according to the approval of the Research Ethics Committee.

### **6.17 Specimen handling**

Samples for local laboratory assessment may be taken at a time convenient for same day processing by the local laboratory. Samples for immunologic or metabolic studies, HLA typing or autoantibodies will be drawn before 12.00 and sent by approved courier to the appropriate laboratory or stored locally for later analysis. At dosing visits blood draw will take place prior to administration of the IMP.

[figure not shown]
**Figure 3 Blood draw schedule:**

	Screening		Treatment					Follow-up				
Visit no:	-2	-1	1	1b	2	3	3b	4	5	6	7	post
Weeks			0		4	8		9	14	20	52	final
Days			0	1	28	56	57	63	98	140	366	dose
Safety blood samples HbA1c & glucose		11			11			11	11	11	11	
DRB1*0401 and A*02	2											
Serum for Aabs	2											
Serum for insulin cell free DNA	8											
Serum for: Aabs, cystatin-c, insulin cell free DNA, other			10					10	10	10	10	
MMTT			25						25			
Blood to accompany skin biopsies												20
Serum for gold concentrations (morning urine also to be sent)			1	1			1	1	1	1	1	
PBMC's T reg assay, T cells, CD4 & CD8 tetramers, Elispots & biobank storage.			64					64	64*		64	
Flow cytometry			2					2	2		2	
Serum for gold concentration before contact hypersensitivity testing												1
Total	12	11	102	1	11	20	1	88	113	22	113	1

\*in subjects with immune responses of interest visit 4, an additional blood sample up to 70mls (35mls for under 18s) may be requested between visit 4 and visit 6.

Volumes for the study within an 8-week period coincide with guidelines of the National Institute of Health (ie blood collection should be <550ml per 8-week period for adults, and no more than 5ml/kg in a single day and no more than 9.5ml/kg in any 8 week period for under 18's) and are those used by the Type 1 diabetes clinical trial consortium, Type 1 Diabetes Trial Net ([www.diabetestrialnet.org](http://www.diabetestrialnet.org)).

**Figure 4 Sample management flowchart**

## 6.18 Laboratory procedures

### 6.18.1 Stimulated secretion of C-peptide

For screening, a post-meal random serum sample in the clinic or urine c-peptide/creatinine ratio will be measured. Patients are provided with a suitable container (boric acid preservative) and asked to void their bladder (and discard this urine) prior to their first meal of the day. They are then asked to substitute their first meal of the day with Ensure Plus and asked not to pass any urine until 2 hours after the Ensure Plus meal and take a sample of urine into the container at this time. These samples will be assayed in the laboratory in Diabetes Research Unit Cymru Laboratories in Swansea for urine c-peptide and creatinine.

During the study secretion of c-peptide will also be tested using the Mixed Meal Tolerance Test method (MMTT). Briefly, the test is performed in the morning (between 7 and 10 AM). The participant must be fasting and have had no food or drink (with the exception of water), and no smoking is permitted from 12 (midnight) or 8 hours prior to the start of the test. Tests should be conducted only if fasting value by capillary blood glucose meter is between 3.9-11.1mmol/L. Participants should withhold taking long acting insulin on the morning of the test. They can take very short acting insulin (e.g. Humalog, Apidra, or Novorapid) up to 2 hours before the test. They can take regular insulin up to 6 hours before the test. If the subject is using an insulin pump, they should be advised to continue their basal regime but not have a bolus.(80)

The procedures are as follows. Start IV line. Obtain baseline blood samples at 0 minutes, and any other test samples required at that visit (e.g. HbA1c, T cell studies, PBMCs islet cell autoantibodies). For each time point blood samples are 1.2 ml fluoride tube for glucose and 1.2 ml serum tube for C-peptide. In addition, for each test the first sample (0 minutes) and the last sample (120 minute for MMTT) will be used to obtain a meter ketone reading, which is recorded. A first blood sample is drawn immediately before the participant starts drinking the liquid meal (formal "baseline samples"). The patient is given the standardized liquid meal: Ensure Plus 6 ml/kg (Maximum 360ml) to be ingested within 5 minutes. Blood samples are drawn at times: 15, 30, 60, 90 and 120 minutes, after the end of ingestion of Ensure Plus (note: time runs from the start of ingestion). After the test is completed, the participant eats and receives insulin as appropriate and prescribed by the local investigator. A urine sample at the 120 minute time point will also be collected for c-peptide creatinine ratio as an alternative marker of insulin production.

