### **4.4 Secondary endpoints**

- T cell responses to C19-A3 GNP as determined by changes from baseline of interferon gamma and IL-10 ELISPOT responses to this peptide in blood following treatment at weeks 0, 9 and 14.
- T cell responses to C19-A3 GNP as determined by changes from baseline of interferon gamma and IL-10 ELISPOT responses to this peptide in draining axillary lymph node before treatment and following the last treatment administration.
- Changes in additional immunological biomarkers (e.g. flow cytometry profiles, T reg assays, autoantibodies, beta cell and T cell free DNA markers) from baseline at week 0, 9 and 14.

- Effects on residual insulin requirement and c-peptide secretion at week 14 as compared to baseline as assessed by a mixed meal tolerance test and a stimulated urine c-peptide test.
- Effects on glycaemic control assessed by blood sugar profiles and HbA1c at week 14 as compared to baseline
- Questionnaires on quality of life and diabetes self-management.

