**Table 1: Schedule of study visits**

Visit number	Screening		Pre V1	Treatment							Follow up				Optional	
	-2	-1		1	1b	1C	2	3	3b	3C	4	Pre V5	5	6	7	any time post dosing
Weeks	These visits can be combined. Treatment must start within 3 months of screening commencing 		A minimum of 72 hours prior to visit 1	0	1 day post visit1	3 to 5 days post visit 1	4	8	1 day post visit3	3 to 5 days post visit 3	9	A minimum of 72 hours prior to visit 5	14	20	52	
Days				0			28	56			63 (or one week post final injection)		98	140 (85 days post final dose)	366 (311 days post. final dose +/- 14 days)	
Informed consent	X															
Study drug administration				X			X	X								
Follow up telephone call 24 hours post IMP				X			X	X								
Physical Exam & ECG	X			X			X	X					X		X	
 Serum for AABs and immune markers				X							X		X		X	
DRB1*0401 genotype	X															
MMTT				X									X		X	
Photographs at injection site				X			X	X			X		X	X	X	
Blood sample to accompany skin studies (optional)								X								
Stitch removal from biopsy site (optional)										X						
urine or random serum c-peptide post meal		X		X									X		X	
72 hour continuous glucose monitoring			Attach CGM	X								Attach CGM	X		X	
Serum for Cystatin C				X							X		X	X	X	
Urinalysis for blood, protein, and beta-2 microglobulin		X		X			X				X		X	X	X	
Serum and urine (morning) sample to measure gold concentrations				X pre dose	X 				X 		X		X	X	X	
T cell (immune biomarker) assays (blood)				X				-			X		X		X	
 LN aspiration 0/3-5d				X		X		X		X						
 Safety blood samples		X		X			X				X		X	X	X	
HbA1c measurement		X		X			X				X		X		X	
Vital signs	X	X		X			X	X			X		X	X	X	
Adverse Event assessment/con meds		X	X	X	X	X	X	X	X	X	X	X	X	X	X	
Urine pregnancy test		X		X			X	X					X	X		
Record of insulin use	X			X			X	X					X		X	
 Blood glucose profile/insulin usage				X			X	X					X	X	X	

Assessment of glycaemic control/review blood sugar recordings				X				X	X					X		X	
Skin biopsy (optional) 																	X
Contact hypersensitivity testing (optional) 																	X
Suction blister (optional) 																	X
XHFS survey				X										X			
ADDQoL				X										X		X	
DTSQs				X										X		X	
DTSQc														X			

Screening can be up to 3 months

Treatment visits 1, 2 and 3 should be every 28 days +/- 3 days and follow up visit 5 should be at 14 weeks +/- 1 week

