### **6.9 Metabolic outcome assessments**

Metabolic assessments will consist of:

- Glucose records and reports of hypoglycaemia (clinical care measurement)
- Insulin dose (clinical care measurement)
- HbA1c level (laboratory test)
- Urine or random serum post-meal c-peptide/creatinine ratio (laboratory test)
- Mixed meal tolerance test (MMTT) (laboratory test)

Laboratory measurements for these will be performed in the laboratories of the Diabetes Research Unit Cymru laboratory, Swansea University.

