### **10.3 Disease exacerbation**

Laboratory tests for exacerbation of  $\beta$ -cell specific autoimmunity are (i) measurement of islet cell autoantibodies (against insulin, GAD-65, IA-2 and ZnT8) at 0 and 14 weeks; and (ii) measurement of pro-inflammatory  $\beta$ -cell specific T cell responses at 0, and 14 weeks. Clinical manifestation of disease exacerbation will be monitored by measurement of secreted C-peptide AUC after MMTT and stimulated urine c-peptide at 0 and 14 weeks ; HbA1c levels (0, 4, 8 and 14 weeks.); and the record of blood sugars and insulin use at each study visit. Disease specific quality of life questionnaires including hypoglycaemia fear (HFS), treatment satisfaction DTSQ and quality of life ADDQoL will be performed at 0 and 14 weeks.

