5.1.2. Secondary outcomes

Differences in the parameters set below will be calculated for each patient and summarised by mean and standard deviations. Potential differences between patients receiving treatment within and outside treatment schedule will also be explored, if required.

- T cell responses to C19-A3 GNP as determined by changes from baseline of interferon gamma and IL-10 ELISPOT responses to this peptide in blood following treatment at weeks 0, 9 and 14.
- T cell responses to C19-A3 GNP as determined by changes from baseline of interferon gamma and IL-10 ELISPOT responses to this peptide in

draining axillary lymph node before treatment and following the last treatment administration (four aspirations: before and after visit 1 and visit 3)

- Changes in additional immunological biomarkers (e.g. flow cytometry profiles, T reg assays, autoantibodies, beta cell and T cell free DNA markers) from baseline at week 0, 9 and 14.
- Effects on residual insulin requirement and c-peptide secretion at week 14 as compared to baseline as assessed by secreted C peptide AUC after a mixed meal tolerance test and a stimulated urine c-peptide test.
- Effects on glycaemic control assessed by blood sugar profiles and HbA1c at week 14 as compared to baseline
- Scores on quality of life and diabetes self-management (week 0 and week 14).

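### The meal-test urine for the week 0 to week 14 C-peptide ratio lacks the pre-meal void and hold required at screening, and two Protocol lists also allow serum for this urine measure.

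*Protocol*

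**What the plan says.** **Endpoint.** Protocol 4.4 compares week 14 with baseline "as assessed by a mixed meal tolerance test and a stimulated urine c-peptide test". SAP 5.1.2 names "secreted C peptide AUC after a mixed meal tolerance test and a stimulated urine c-peptide test", with a difference per patient summarised by mean and standard deviation. Protocol 10.3 also lists "stimulated urine c-peptide at 0 and 14 weeks" among the clinical markers of disease exacerbation. Protocol 12.1.1 ranks the urine ratio as an alternative to the meal-test AUC.

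**Collection.** In the screening paragraph of Protocol 6.18.1, patients are "asked to void their bladder (and discard this urine) prior to their first meal of the day", then drink Ensure Plus and pass no urine until the sample two hours later. In the meal-test procedure of the same section the urine instruction is "A urine sample at the 120 minute time point will also be collected for c-peptide creatinine ratio as an alternative marker of insulin production". Protocol 12.2.1 likewise mentions only a sample after 120 minutes. Neither place states a void before the drink or a hold during the test.

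**Specimen.** The row in Protocol Table 1 reads "urine or random serum c-peptide post meal" and is marked at visits -1, 1, 5 and 7. Protocol 6.9 lists the same choice as a metabolic outcome, under the label of a creatinine ratio. Protocol 6.18.1 introduces the choice for screening only. The corresponding row of the SAP schedule lists urine alone.

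**The concern.** A post-meal urine ratio reflects stimulated secretion only if the bladder was empty when the meal began. Without that step, the 120-minute sample pools urine formed during the fast with urine formed after the drink, in a proportion set by when the patient last voided. If that time differs between visit 1 and visit 5, the ratio moves although secretion has not.

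The specimen wording is a separate matter. A serum concentration in pmol/l and a urine ratio in nmol/mmol (the units in Protocol 6.2) cannot be subtracted, and neither document says how a serum value would enter a urine endpoint.

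At stake is the reading of individual changes in about 8 patients. Protocol 3.4 requires residual C-peptide so that disease exacerbation can be monitored, and 10.3 names this test for that purpose.

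**Working it through.** The documents give no precision, target change or error figure for the urine ratio, so there is nothing of the plan's own to reproduce. The check asks how far an unchanged patient's ratio can move.

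**Inputs from the documents**
- Post-meal collection: 2 hours (6.18.1).
- Fast before the meal test: from midnight or 8 hours, water allowed (6.18.1). 8 hours is used as the upper limit for retained urine.
- Patients: 8 in a single group (Protocol 14).

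**Assumptions, not in the documents**
- f, the fasting ratio divided by the stimulated ratio: 0.3 to 0.6, the same at both visits.
- T, the hours of pre-meal urine still in the bladder when the drink starts: 0 to 8.
- Constant creatinine output and no true change in secretion.

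**Formula.** With constant creatinine output, each hour of urine has equal weight, so

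R = measured ratio / true stimulated ratio = (f × T + 2) / (T + 2).

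**Case 1: bladder emptied at week 0 (R = 1), T hours retained at week 14.** False change = R − 1. In the reverse order it is 1/R − 1.

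| f | T = 2 h | T = 4 h | T = 8 h |
|---|---|---|---|
| 0.3 | R 0.65: −35% (reverse +54%) | R 0.533: −47% (+88%) | R 0.44: −56% (+127%) |
| 0.5 | R 0.75: −25% (+33%) | R 0.667: −33% (+50%) | R 0.60: −40% (+67%) |
| 0.6 | R 0.80: −20% (+25%) | R 0.733: −27% (+36%) | R 0.68: −32% (+47%) |

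The extremes are (0.6 × 2 + 2)/4 = 0.80, a 20% false fall, and (0.3 × 8 + 2)/10 = 0.44, a 56% false fall.

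**Case 2: no void at either visit, 6 h retained then 8 h.** False change = R(8)/R(6) − 1.
- f = 0.3: 0.44/0.475 − 1 = −7.4%
- f = 0.5: 0.60/0.625 − 1 = −4.0%
- f = 0.6: 0.68/0.70 − 1 = −2.9%

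**Case 3: equal retention.** R cancels and the relative change is unbiased.

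**Group mean.** If one of 8 patients is discordant as in Case 1 with 8 h retained, the mean percentage change moves by −56/8 = −7.0 points at f = 0.3 and −32/8 = −4.0 points at f = 0.6.

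**After the fix.** T = 0 at both visits gives R = 1 at both and no false change, whatever f is.

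**Specimen, by comparing the texts.** The endpoint statements (Protocol 4.4, 10.3, 12.1.1; SAP 5.1.2) and the SAP schedule say urine. Protocol Table 1 and 6.9 permit serum at visits 1 and 5. The meal test is scheduled at both visits and its 120-minute urine is due whichever option that row is met by.

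**The case against.** The case on the other side is substantial.

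- **Silence is not a rule against voiding.** The meal-test text presents itself as a brief account, and Protocol 6.7 promises a laboratory manual that is not among the documents. Morning urine for gold, urinalysis and a pregnancy test are also due at visits 1 and 5, so a void before the drink may well happen. This stands as a reason for caution about how often the problem would arise. It does not supply the missing timing, since none of these voids is tied to the start of the meal.
- **The screening procedure may be meant for every urine test.** Table 1 gives the post-meal row and the meal test separate lines, so there could be two collections at visits 1 and 5, one of them with the void. The text allows that reading but does not state it. It would also leave open which urine enters the endpoint.
- **Similar conditions limit the error.** The fast and the morning start are the same at both visits, which makes extreme differences in retention less likely. This stands, and Cases 2 and 3 show its effect. Equal retention still leaves the sample diluted with fasting urine. With f = 0.4 and 8 h at both visits, halving stimulated output with fasting output unchanged takes the measured ratio from 0.52 to (0.4 × 8 + 0.5 × 2)/10 = 0.42, a 19% fall in place of 50%.
- **Impact is limited.** The measure is secondary and descriptive, SAP section 4 says the sample is not powered for before-after differences, and the serum AUC is reported beside it. The exacerbation analysis in SAP 5.1.1 lists only autoantibodies and T cell responses. All of this stands.

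A reader might infer that a patient tested by serum at one visit has no urine change at all. The documents do not support that, because the 120-minute urine is still due at both meal tests. Nor does a switch of specimen create a large false change: the serum value simply cannot be used in the difference. It would also be too strong to say that the error matches the decline the trial is looking for, since no target decline is stated.

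**Conclusion.** Two points hold on the text. The meal-test urine is specified without the void and hold that the Protocol itself requires at screening. Protocol Table 1 and 6.9 also conflict with the urine endpoint and with the SAP schedule.

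The size of the first depends on undocumented values of f and on voiding that differs between visits. The false fall is 20% to 56% in the discordant case, about 3% to 7% for 6 versus 8 hours, and zero in relative terms when retention is equal and f is stable. The 20% to 56% range shows what the written procedure permits in one patient; it is not an estimate of what will typically occur. The second point is an inconsistency to be removed and adds no numerical bias of its own.

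The serum AUC and the primary safety outcome are untouched. The correction is worth making because it is nearly free and the ratio is also named for monitoring exacerbation.

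**What to change.** - **Protocol 6.18.1, meal-test procedure (and 12.2.1 by reference):** empty the bladder and discard the urine immediately before the Ensure Plus, pass no urine until the 120-minute sample, and record the void time.
- **Protocol Table 1 and 6.9:** limit the random serum option to screening visit -1.
- **SAP 5.1.2:** state that the change uses the 120-minute urine ratio at visits 1 and 5. Keep samples without a recorded pre-meal void, flag them, and show the summary with and without them.

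The cost is one extra instruction and one recorded time per meal test, plus the wording changes. No visit or sample is added.

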### **6.18.2 Mechanistic assays for the assessment of immune biomarkers**

#### **6.16.2.1 Cytokine ELISPOT**

Cytokine ELISPOTS for the detection of IFN- $\gamma$  and IL-10 producing CD4 T cells in response to PPI C19-A3 and other islet autoantigenic peptides will be performed as previously described (24, 79, 81). These assays provide a means to monitor potentially favourable changes in the immune response to PPI C19-A3 (eg a shift from IFN- $\gamma$  to IL-10 secreting cells). These will be performed on both peripheral blood mononuclear cells and LN aspirate cells as well as on skin derived leukocytes where an optional skin blister aspiration sample is provided.

#### **6.18.2.2 Storage of peripheral blood mononuclear cells for additional T and B cells assays and immune gene profiling**

Blood samples will be taken at 0, 9 and 14 weeks and the peripheral blood mononuclear cells cryopreserved as well as samples stored for later DNA analysis. These will be performed by the T1D UK Mechanistic Core laboratories.

#### **6.18.2.3 Storage of serum for islet autoantibody and cell free DNA studies.**

Blood will be taken at 0, 9 and 14 weeks and spun down for serum which will be aliquoted and frozen at -80C. Sample will be stored for later islet autoantibody and cell free DNA

analysis. Islet autoantibodies to GAD, IA-2 and ZnT8 will be measured in the Diabetes Research Unit Cymru Laboratories, Swansea University and cell free DNA assays (for beta cell and T cell apoptosis) will be performed via the T1D UK Mechanistic Core laboratories.

### **6.18.3 Analysis of skin biopsies.**

In individuals who agree to provide a skin biopsy from the first injection site anytime post-dose, this material will be divided for immunohistology/gold distribution analysis and RNA extraction for RNA seq/QPCR.

## **7 Risk Mitigation Strategy**

**Communication between trial sites.** The clinical research teams of the two sites involved will be in weekly telephone contact (teleconference) during the recruitment and dosing periods. All adverse reactions will be discussed and information shared.

**All serious adverse events will be shared within 24 hours with the other recruiting site.**

**Sentinel dosing.** The first patient dosed with GNP-peptide will be observed for 6 hours post dose. Temperature, blood pressure and heart rate will be recorded at the following intervals post injection: 15 mins, 30 mins, 45 mins, 1 hour, 1 hour 30mins, 2 hours, 2 hours 30 mins, 3 hours, 4 hours, 5 hours and 6 hours. The injection site will be observed at the following intervals post injection: 5mins, 10 mins, 15 mins, 30 mins, 45 mins and 1 hour. A follow-up phone call will be made to the subject 24 hours after the first dose. No additional patients will be able to be recruited until this 24 hour period is completed (“lock-out period”).

If no serious adverse events are observed, subsequent subjects will also be observed for 6 hours after their first injection. If no serious adverse events are observed, then subjects will be observed for a minimum of 1 hour post dose, or 2 hours if there are any symptoms of signs of hypersensitivity. This time period has been chosen as the only anticipated severe reactions is one of hypersensitivity which, if systemic, would be apparent within 60 mins of intradermal dosing. See section 10.2 for further discussion of hypersensitivity.

Each subject will be contacted by telephone 24 hours after each dose.

The trial manager will communicate with clinical staff by email and telephone to keep both sites up to date with screening and recruitment activity. Weekly teleconferences between sites will take place during the screening and recruitment phase and the trial manager will inform clinical staff at both sites when the first patient is going to be dosed and report to them afterwards regarding whether any AE's were experienced. This will negate the possibility of two subjects starting treatment on the same day. Close communication between sites will be maintained throughout the trial and details of any adverse reactions will be communicated to the other trial treatment site by email, in addition to the standard pharmacovigilance procedures.

